11 STUDY ASSESSMENTS AND PROCEDURES

All study procedures and their timing are summarized in the Schedule of Events (Table 1).

All visits, except the Follow-up Phone Call, Visit 2 (Week 1/Day 7) and Visit 9 (Week 16/Day 112) should be conducted within +/-3 days from the scheduled visit day relative to the randomization visit (unless otherwise indicated). The Follow-up Phone Call should be conducted within +1 day from the randomization (Visit 1; Week 0/Day 0) visit date. The Visit 2 (Week 1/Day 7) study drug administration must be conducted on the scheduled visit date relative to the date of randomization. This visit cannot be conducted early and, should it be conducted late, the visit schedule must be adjusted based on the actual date of Visit 2 (Week 1/Day 7). The Visit 8 endoscopy and biopsy (not the visit, but the endoscopy and biopsy only) can be conducted within +/- 7 days of Visit 8, and Visit 9 (Week 16/Day 112) should be within +/-7 days from the original or adjusted scheduled visit date.

All study visits occurring after randomization (Visit 1, Week 0/Day 0) should be based on the Visit 1 study visit date, or the adjusted visit schedule in the event of a delayed Visit 2 (Week 1/Day 7). During the 12-week randomization period, subsequent to Visit 2 (Week 1/Day 7), if a study visit occurs no more than a maximum of 4 days outside of the visit window (± 7) the study drug can be administered and the next visit scheduled in accordance with the original or adjusted visit calendar. If a late study visit should occur more than 4 days outside of the study visit window the study drug should not be administered and a protocol deviation recorded. Under no circumstances should any 2 doses of study drug be administered within fewer than 7 days of each other.

If a subject misses 2 consecutive doses of study drug the subject should be terminated from the study after consultation with the Sponsor and should complete the Early Termination visit. The Final Study Visit should be conducted at least 6 weeks (+/- 7 days) after the last study administration of study drug. The Final Study Visit is not required if the last administration of study drug occurred 6 or more weeks prior to the Early Termination visit.

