11.4 EARLY TERMINATION (ET)

Early Termination visits should be conducted for randomized subjects (subjects who received double-blind treatment) who discontinue participation in the study. Early termination visit procedures are not required for subjects who do not receive study drug and are therefore considered screen failures.

- Document visit in EDC system.
- Collect vital signs.
- Measure body weight.
- Perform physical examination to include an examination of general appearance; HEENT; lymph nodes; respiratory; cardiovascular; gastrointestinal; musculoskeletal; neurological, psychological and dermatological systems.
- Collect blood and urine for clinical laboratory testing.
- Collect blood sample for PK, ADA and biomarkers. Record date and actual time of sampling.
- Perform serum pregnancy test on FOCBP.
- All attempts should be made to collect a final iVYLISA GIP stool sample, if the sample was not collected within 3 days prior to the scheduled Early Termination visit.
- Assess AEs.
- Monitor for changes to concomitant medications.
- Allow subject to complete SF-12 v. 2 and EQ-5D.
- Complete PGA.
- Allow the subject to complete the Patient Global Assessment of Disease (PtGA), BEFORE study drug administration.

- Perform endoscopy and collect biopsy specimens within 7 days of the Early Termination visit unless not indicated based on the subject's condition, at the PI's discretion.
- Schedule the Final Study Visit. The Final Study Visit is not required if the Early Termination visit occurs 6 or more weeks after the last study drug administration.

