15.3 CLINICAL LABORATORY RESULTS

Laboratory parameters, as listed in Appendix B and the Central Laboratory Manual or equivalent document, will be obtained at times indicated on the Study Schedule of Study Procedures (Table 1). Blood and urine samples collected at the Screening Visit will require a minimum 8-hour fast.

A subject with a clinically significant laboratory finding identified at the Screening Visit should not participate in the study.

All clinically significant findings during the study should be followed until resolution or until the finding is clinically stable. Subjects may be withdrawn from the study if the Investigator or Sponsor deems the clinically significant finding compromising to the subject's safety.

Detailed information regarding the collection and handling of clinical laboratory specimens, including blood draw totals for each visit and instructions for re-testing of missing or compromised specimens, can be found in a separate Central Laboratory Manual or equivalent document supplied by the central clinical laboratory.

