20.2 SUBJECT WITHDRAWAL

All subjects are free to withdraw from participating in this study at any time and for whatever reason, specified or unspecified, without prejudice.

Reasons for withdrawal (subjects refuse to return for any remaining study visits) or discontinuation (subjects who prematurely stop the active treatment) at any time during the study may include but are not limited to the following:

- Safety reasons, either at the discretion of the Investigator or at the subject's request. In particular, subjects will be discontinued from the study if they develop severe complications of celiac disease that require intensive treatment (EATL, perforation, etc.).
- Protocol violations at the discretion of the Sponsor.
- Subject noncompliance to study procedures or schedule
- Concomitant therapy that could interfere with the results of the study (the Investigator will report all such information on the eCRFs and decide, in accordance with the Sponsor, whether the subject is to be withdrawn).
- Subject's decision to withdraw at any time.

Subjects who withdraw prior to receiving the study drug are considered screen failures.

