20.2.1 Withdrawal Procedures

If for any reason a subject is withdrawn or discontinues before completing the final visit, the reason for termination must be recorded in the source documents and reported on the appropriate eCRF. All data gathered on the subject prior to termination will be made available to the Sponsor.

Subjects discontinuing study drug should continue to be fully evaluated per the protocol event schedule, when possible, for safety purposes. However, if the subject discontinues before

Week 6, the second biopsy will not be collected. If a discontinuation occurs on or after Week 6, the second biopsy will be obtained.

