8.8.2 Clinical laboratory tests

Clinical laboratory tests include haematology, clinical chemistry, and urinalysis panels. The complete list of clinical laboratory parameters is presented in Table 3 below.

Table 3 Clinical laboratory tests

Haematology	Clinical Chemistry	Urinalysis
Basophils (absolute)	Alanine Aminotransferase (ALT)	Blood Cells (Erythrocytes, Leukocytes)
Basophils/Leukocytes	Albumin	Glucose
Eosinophils (absolute)	Alkaline Phosphatase	Ketones
Eosinophils/Leukocytes	Aspartate Aminotransferase (AST)	Microscopic evaluation (i.e. Bacteria, Squamous Epithelial Cells, Mucous Fiberis, Urine, Crystals)
Haematocrit	Bilirubin (Total)	Protein
Haemoglobin	Calcium	
Lymphocytes (absolute)	Chloride	
Lymphocytes/Leukocytes	Creatinine	
Monocytes (absolute)	Glucose	
Monocytes/Leukocytes	Lactate dehydrogenase (LDH)	
Neutrophils (absolute)	Potassium	
Neutrophils/Leukocytes	Protein (Total)	
Platelet Count	Sodium	
Red Blood Cell (RBC) count	Urea (BUN)	
White Blood Cell (WBC) count		
Anti-tissue transglutaminase (tTG) IgA and IgG		
Anti-tTG6 IgA and IgG		

Clinical laboratory parameters will be obtained at times indicated in the study schedule ([Appendix 1](#)). Blood and urine samples collected at the Screening Visit will require a minimum 8-hour fast.

All clinically significant findings during the study should be followed until resolution or until the finding is clinically stable. Subjects may be withdrawn from study drug if the Investigator or Sponsor deems the clinically significant finding compromising to the subject's safety; however, these subjects will continue to be followed-up per protocol, unless consent is withdrawn.

Detailed information regarding the collection and handling of clinical laboratory specimens, including blood draw totals for each visit and instructions for re-testing of missing or

compromised specimens, can be found in a separate Central Laboratory Manual or equivalent document supplied by the central clinical laboratory.

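### Protocol section 11 says a subject who misses two consecutive doses should leave the study, 20.2.1 keeps subjects off drug on schedule, and the exit-endoscopy text conflicts with the Week 6 biopsy rule

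*Protocol*

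**What the plan says.** **Missed doses.** Protocol section 11: "If a subject misses 2 consecutive doses of study drug the subject should be terminated from the study after consultation with the Sponsor". Such a subject has an ET visit. On the last contact, the same section says: "The Final Study Visit should be conducted at least 6 weeks (+/- 7 days) after the last study administration of study drug". It waives that visit only if ET falls 6 or more weeks after the last dose.

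**Stopping drug.** Protocol 20.2 uses two terms: "Reasons for withdrawal (subjects refuse to return for any remaining study visits) or discontinuation (subjects who prematurely stop the active treatment"). Protocol 20.2.1 then says: "Subjects discontinuing study drug should continue to be fully evaluated per the protocol event schedule, when possible, for safety purposes".

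**A parallel case.** For significant laboratory findings, Protocol 15.3 says: "Subjects may be withdrawn from the study if the Investigator or Sponsor deems the clinically significant finding compromising" to safety. SAP 8.8.2 restates this as withdrawal from study drug and adds that "these subjects will continue to be followed-up per protocol, unless consent is withdrawn".

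**Exit endoscopy.** Protocol 11.4: "Perform endoscopy and collect biopsy specimens within 7 days of the Early Termination visit unless not indicated based on the subject's condition". The PI makes that judgement. Table 1 footnote 5 and Appendix B item 9 say much the same. None of the three mentions Week 6. Protocol 20.2.1 says that if the subject discontinues before "Week 6, the second biopsy will not be collected". Protocol 22.3 and SAP 8.2.3 repeat this for stopping study drug and exclude these subjects from the per protocol (PP) population.

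**The concern.** A subject who misses two infusions but is willing to attend falls under both section 11 and section 20.2.1, and nothing ranks them. The choice decides how long symptom data are collected. GSRS, CeD-GSRS, BSFS and CeD PRO are analysed in the ITT population and planned to Week 16. If section 11 is followed, the repeated-measures models have no observed score for the lost weeks and rely on missing-at-random. Missed infusions may be linked to illness or tolerability, so that assumption is not a comfortable one, and the lost scores belong to a schedule already planned.

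The endoscopy conflict is separate. A subject terminated early could have an invasive procedure, with up to 11-13 specimens (Protocol 13.2), that three other places say should not be done for the study.

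The date on which drug counts as stopped is also undefined. That date decides whether the second biopsy is taken and whether the subject enters the PP population used for the primary analysis.

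**Working it through.** **Inputs.** Doses at Weeks 0, 1, 2, 4, 6, 8 and 10 (Protocol Table 1 and section 6). GSRS weekly through the Final Study Visit (13.3.2), which gives 16 post-baseline scores, 12 of them through Week 12. Final Study Visit 6 weeks after the last dose (sections 11 and 11.3.1). The eDiary is collected at that visit (11.3.1).

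**The plan's own figure.** For a full course, last dose Week 10 + 6 = Week 16, as stated.

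**Assumptions.** The Week 0 dose is given. ET takes place at the nominal visit of the second missed dose. Diaries run to the Final Study Visit.

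**Formulas.** F = last dose week + 6. Lost of 16 = 16 − F. Lost of 12 = max(0, 12 − F). Diary days lost = 112 − 7F. If diaries stop at ET, replace F by the ET week.

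| Doses missed (weeks) | Last dose | ET | F | Lost of 16 | Lost of 12 | Diary days lost | If diaries stop at ET: of 16 / of 12 |
|---|---|---|---|---|---|---|---|
| 1+2 | 0 | 2 | 6 | 10 | 6 | 70 | 14 / 10 |
| 2+4 | 1 | 4 | 7 | 9 | 5 | 63 | 12 / 8 |
| 4+6 | 2 | 6 | 8 | 8 | 4 | 56 | 10 / 6 |
| 6+8 | 4 | 8 | 10 | 6 | 2 | 42 | 8 / 4 |
| 8+10 | 6 | 10 | 12 | 4 | 0 | 28 | 6 / 2 |

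- ET falls 2 to 4 weeks after the last dose, so the Final Study Visit is never waived on this timing.
- The Week 12 score is lost in four of the five patterns and the Week 16 score in all five.
- The 7-day window on the Final Study Visit moves each figure by at most 1.
- Weeks 1+2 is unlikely: under section 11 a late Visit 2 shifts the schedule and does not count as missed. Without it the range is 4 to 9 of 16 and 0 to 5 of 12.
- One affected subject is 1/8 = 12.5% of the planned placebo arm or 1/16 = 6.25% of the AMG 714 arm.

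**Endoscopy.** In patterns 1+2 and 2+4, ET is at about Week 2 or 4, before Week 6 on any reading of the stopping date. In 4+6 and 6+8 the last dose is at Week 2 or 4 but ET is at Week 6 or 8, so the answer depends on which date counts. In 8+10 the last dose is at Week 6, so there is no conflict. The conflict therefore covers two patterns if the stop is dated at the second missed dose, and four if it is dated at the last dose.

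**The case against.** **Both rules are softened.** Section 11 says should, after Sponsor consultation; 20.2.1 says when possible and for safety purposes. Section 20.2 also lists noncompliance with procedures or schedule as a reason for withdrawal or discontinuation, so section 11 could be read as the specific rule and 20.2.1 as the general one. A reader might infer that everyone who misses two doses is removed automatically; the text does not say that. What stands is that no text states which rule governs. The SAP 8.8.2 wording concerns laboratory findings, so it shows a workable solution and does not decide this case.

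**The Week 6 biopsy rule is specific and the ET text is general.** A careful PI could use discretion to skip the endoscopy. But that discretion is tied to the subject's condition, and sites following 11.4, Table 1 or Appendix B would not see the limit.

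**ET may be late.** Section 11 allows dosing up to 4 days outside the window. With a 3-day window, a Week 4 dose missed through lateness is settled only after Day 28 + 3 + 4 = 35, and an endoscopy 7 days later is near Day 42. The procedure could then fall near Week 6, but drug still stopped before Week 6, so SAP 8.2.3 excludes the subject from PP anyway.

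**An early biopsy has a use.** A reader might infer that it is worthless. It is not: SAP 8.7.5 allows earlier post-dose values in exploratory PK/PD plots. It cannot enter the PP primary or secondary analyses.

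**Impact is limited.** Affected subjects keep their earlier scores in the ITT models. PGA, PtGA, SF-12 and EQ-5D are still collected at ET. Some who miss infusions may also miss visits. All of this stands.

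**Conclusion.** Both conflicts are in the current text and should be removed. If section 11 is followed and diaries run to the Final Study Visit 6 weeks after the last dose, 4 to 9 of 16 weekly GSRS scores are lost by design (0 to 5 of the 12 through Week 12), or 10 and 6 in the unlikely Weeks 1+2 pattern. These figures depend on when diaries end. Section 20.1 treats withdrawn subjects as completing at ET, and if diaries stop there the loss is 6 to 14 of 16, with 14 again from Weeks 1+2.

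The exit-endoscopy conflict is certain for drug stopped before Week 6 and extends to two more patterns while the stopping date is undefined.

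A reader might infer a loss of power for the primary endpoint or shortened safety follow-up. Neither is supported: the documents give no frequency of missed doses, and terminated subjects still have the same 6 weeks of post-dose follow-up as completers.

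**What to change.** 1. In section 11, state that missing two consecutive doses stops study drug only. Visits and diaries continue to Week 16 unless consent is withdrawn.
2. Define the stopping date once, as the visit of the second missed dose, and repeat it in SAP 8.2.3. With this choice, patterns 4+6 and 6+8 keep biopsies that now qualify at Week 6 or later; dating the stop at the last dose would lose them.
3. In 11.4, Table 1 footnote 5 and Appendix B item 9, limit the study exit biopsy to drug stopped on or after Week 6. Take it within 7 days of the stopping visit, as ET timing is now, even though the subject stays in the study. Without this anchor, removing the ET visit would leave the biopsy with no date. The carry-forward rule in SAP 8.2.2 is unchanged. A clinically indicated endoscopy remains the PI's decision.

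**Result.** No weekly score is lost by design, and the plan no longer calls for a study endoscopy when drug stops before Week 6.

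**Cost.** Protocol amendment wording and one line in the SAP. Extra visits per affected subject are the scheduled visits after ET minus the one Final Study Visit: 5, 4, 3, 2 or 1 in the table's order, all already planned. Extra diary days are 28 to 70 (42 to 98 if diaries now stop at ET: 112 − 70 and 112 − 14). No endoscopy is added. Week 16 is 10 to 16 weeks after the last dose, so the 6-week minimum is met.

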11.1 ASSESSMENTS AT EACH VISIT

All subjects who sign an Informed Consent Form will be assigned a unique subject number. This number will be used for identification purposes for all study visits.

All subjects who sign an Informed Consent but do not enter the study must have a reason recorded as to why randomization into the study did not occur. This information will be input into the Electronic Case Report form (eCRF).

Retesting of screening evaluations is permitted once for each test without prior approval from the Sponsor. Additional retesting may be permitted on a case by case basis after consultation with the study Sponsor.

Rescreening of subjects is permitted at the discretion of the Investigator.

11.1.1 Screening Visit

- Obtain informed consent.
- Register the visit in the electronic data capture (EDC) system.
- Review inclusion/exclusion criteria. For interpretation of hepatitis testing results, see Appendix F.
- Document demographics and medical history.
- Collect vital signs.
- Measure height and weight.

NOTE: Height will be measured at the Screening Visit only. Subjects will not wear shoes during height measurement. Body weight is measured at all visits. Body weight should be obtained while the subject is wearing light weight clothing. Shoes will not be worn during body weight measurement.

- Document prior and concomitant medications (including prescription and over-the-counter medications, nutritional supplements, and herbal preparations taken within 30 days of screening).
- Perform physical examination to include an examination of general appearance; head, eyes, ears, nose, throat (HEENT); lymph nodes; respiratory; cardiovascular; gastrointestinal; musculoskeletal; neurological, psychological and dermatological systems.
- Perform 12-lead electrocardiogram (ECG).

NOTE: A 12-lead resting ECG will be obtained from all subjects at the time of screening. ECGs will be recorded after the subject has been supine for approximately 5 minutes. Each 12-lead ECG will be evaluated by an appropriately qualified physician at the study site. ECG data will be evaluated using the following categories:

- Normal
- Abnormal, not clinically significant
- Abnormal, clinically significant

Any suspected cardiovascular AE should be followed with an additional ECG at the discretion of the Investigator.

- Collect stool sample for iVYLISA GIP testing.
- Collect blood and urine specimens for clinical laboratory testing (see Appendix B and/or Central Laboratory manual for the parameters).

NOTE: HLA DQ typing is only required when this information is not already part of the subject's available existing medical record.

- Collect blood for serum pregnancy test for FOCBP.
- Begin assessment of AEs.
- Schedule subject for endoscopy procedure.

When the screening clinical laboratory test results are received, they must be reviewed by the Investigator or appropriate qualified designee for clinically significant abnormalities.

If no clinically significant abnormalities or exclusions are found, the site should proceed with the scheduled endoscopy and biopsy (or proceed directly to the endoscopy and biopsy without having lab results if required due to logistical or clinical considerations). If clinically significant abnormalities are found, retesting of the subject shall occur at the discretion of the Investigator or designee physician. Retesting is permitted one time for each laboratory parameter. Additional testing may be permitted after consultation with the Sponsor's appropriate qualified designee. If the clinically significant abnormalities resolve, the subject can proceed with the scheduled endoscopy and biopsy.

11.2 12-WEEK RANDOMIZATION PERIOD

11.2.1 Randomization and Dosing preparation

The unblinded pharmacist or unblinded study staff member assigned to the receipt and preparation of study drug materials (see Section 18 for guidance on study drug blinding) should register medication dispensing in the EDC system at least 24 hours before the first dosing visit to obtain a randomized treatment assignment for the subject and subsequent vial distribution.

Study drug must be thawed overnight and prepared in advance of the study visit as per the guidance in Section 18 of this protocol.

11.2.2 Visit 1 (Week 0/Day 0)

- Review inclusion/exclusion criteria.
- Document visit in the EDC system.
- Allow subject to complete SF-12 v. 2 and EQ-5D.
- Assign e-diary and allow subject to complete the first weekly GSRS and daily CeD PRO.
- Collect vital signs.
- Measure body weight.
- Perform physical examination to include an examination of general appearance; HEENT; lymph nodes; respiratory; cardiovascular; gastrointestinal; musculoskeletal; neurological, psychological and dermatological systems.
- Complete Physician Global Assessment (PGA), BEFORE study drug administration.
- Allow the subject to complete the Patient Global Assessment of Disease (PtGA) BEFORE study drug administration.
- Collect blood and urine for clinical laboratory testing.
- Collect blood sample for PK, ADA and biomarkers BEFORE start of study drug administration. Record date and actual time of sampling.
- Collect Whole Blood for Flow Cytometry.
- Collect blood cell pellet.
- Collect iVYLISA GIP stool sample. The stool sample will be produced within 3 days prior to, or after, the scheduled study visit (± 3 day window).
- Perform urine pregnancy test on FOCBP.
- Administer study medication. See section 18 for administration procedures.

NOTE: Subject should remain in the clinic for a minimum of 1 hour after the end of study drug administration to monitor for new AEs and collect the second PK sample.

- Assess AEs.
- Monitor for changes to concomitant medications.
- Dietitian assessment of the GFD. This assessment can be conducted by phone provided it is conducted within the allotted visit window.
- Collect blood sample for PK 1 hour after END of infusion of study medication. Record date and actual time of infusion beginning, end and sampling.
- Remind subjects to complete the BSFS at each occurrence of a bowel movement and the CeD PRO daily.
- Remind subject to complete the weekly GSRS.
-

